Table 2 – intervention design. ECG: electrocardiogram. ePRO: electronic patient-reported outcome. NT-proBNP: N-terminal prohormone of brain natriuretic peptide. KCCQ-12: Kansas City Cardiomyopathy Questionnaire. EQ5D: EuroQol 5-dimension questionnaire. HeartQoL: Health-related quality of life questionnaire. PHQ9: patient health questionnaire-9. HLS-EU-Q16: European Health Literacy Survey Questionnaire. EHFSB-9: European Heart Failure Self-care Behaviour scale revised into a nine-item scale. SUTAQ: Service User Technology Acceptability Questionnaire. WPAI : work productivity and impairment.

Health economic analysis

The costs considered for the cost-effectiveness analysis are direct costs of the smartphone-based digital support intervention and the care utilisation recorded during the inclusion of the trial. The costs for the digital support intervention consist of costs for data management using the application, costs for devices that are provided in selected patients (blood pressure monitor, weighing scale), and personnel costs for inclusion and time spent on follow-up of alarms.

Information on care utilisation will be collected at the end of the trial. Former studies have demonstrated that hospitalisation costs are the key driver of HF-related costs (7,8). This study will thus focus on reduction in length of hospital stay and reduction in rehospitalisations after initial hospitalisation. The 30-day and 90-day rehospitalisation rates will be assessed. All hospital-related costs will be collected from the hospital billing and financial departments. A distinction will be made between scheduled and non-scheduled hospitalisations. Scheduled hospitalisations for elective procedures and scheduled visits with the cardiologist or general practitioner will not be included in the cost-evaluation.

Implementation cost and cost-effectiveness will be assessed in this trial following a pre-post economic model. A historical cohort of all patients hospitalised for HF on a cardiology ward in 2019 in all participating centres will be assessed for comparison. Hospital bills and hospital administrative data based on the international classification of disease (ICD)-codes will be collected. Propensity matching will be applied.

QOL and healthcare-related costs will be collected in selected patients refusing to participate in the smartphone intervention.

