Cost reduction between the intervention group, the historical cohort, and the participation refusals will be calculated. Costs and outcomes (utilities) will be compared by calculation of the incremental cost-effectiveness ratio (ICER) (ICER = $(\text{cost}_{\text{intervention group}} - \text{cost}_{\text{historical cohort}}) / (\text{effectiveness}_{\text{intervention group}} - \text{effectiveness}_{\text{historical cohort}})$). The incremental cost represents the difference in total average cost per patient between the intervention group and the historical cohort or the participation refusals. Effectiveness will be calculated by comparing QOL in the intervention group versus the participation refusals.

Study endpoints

The endpoints that will be assessed are summarized in Table 3. As specified before, the objectives of the study are to demonstrate positive implementation measures (e.g. feasibility) as well as to demonstrate cost-effectiveness. Secondary objectives include assessment of clinical impact, based on measurement of clinical endpoints as specified in Table 3. Implementation outcome variables will be assessed using a mixed-method design. Patient and caregiver parameters will be calculated (e.g. time spent using the application). Questionnaires will be used to assess patient variables. Semi-structured interviews in a selection of patients and caregivers will be performed to assess further outcome variables regarding implementation.

Implementation outcome variables	
Feasibility and patient acceptability	SUTAQ, semi-structured interviews.
Caregiver acceptability and burden of care	SUTAQ, semi-structured interviews, daily time spent by case nurses using the platform
Adoption and sustainability	Number and percentage of patients refusing inclusion, of patients continuing application usage after 6 months. Total time-percentage ratio of patients using the application throughout the trial.
Implementation cost	Cost-related data: healthcare resource use, hospital days, tests, procedures, health expenditure. Cost-effectiveness: healthcare cost data, WPAI questionnaire, ICER. Cost of hospital stay at inclusion.
Quality of life, literacy and patient self-care	KCCQ-12, EQ5D, HeartQoL, PHQ9, HLS-EU-Q16, EHFSB-9, SUTAQ.
Clinical outcome measurement	
Combined endpoint	Unplanned CV readmission and all-cause mortality

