In recent years, many studies have investigated telemonitoring and digital support of HF in different modalities (2–5) in a RCT setting using strict inclusion and exclusion criteria. Many of these trials had successful results and could prove the superiority of the digital support intervention on their primary endpoints. However, due to the RCT nature, it remains unclear how easily these results will translate into a real-life healthcare context. One trial investigated implementation of a smartphone-based HF digital support intervention and could report a 50% decrease in HF-related hospitalisations (10). However, this trial was conducted in Canada and is thus specific for the Canadian healthcare context.

By its implementation design, the Bedicare-HF study aims to take digital support of HF to the next step towards implementation. A large advantage is that it is an all-comers study, in which all patients meeting the inclusion criteria will be asked to participate, and that information on those who refuse participation will be available for analysis. This information will be of direct use for later implementation in the healthcare setting. An intrinsic limitation is that it is specific to the European and even Belgian healthcare context and that the results about implementation cannot necessarily be generalised to other healthcare systems. Another limitation is that due to the nature of the trial setup, no distinct comparator group is available and a historical cohort will need to be used. However, we believe that the strength of this trial is in its pragmatic design and the value of information not only on trial participants but also on trial non-participants.

A particular challenge to the Bedicare-HF trial will be the European GDPR-context and medical device regulations. The collaboration between a commercial partner and multiple hospitals means that sensitive data will need to be securely exchanged. Overcoming this challenge can directly yield useful information on the implementability of this technology.

In Belgium, there is currently no framework for reimbursement of telemonitoring and digital support of HF, neither non-invasively nor invasively. Recently, a reimbursement framework was approved for reimbursement of medical smartphone applications. If the Bedicare-HF intervention is shown successful, this will have direct implications for reimbursement of HF digital support and telemonitoring in Belgium.

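### The utility ICER is printed against the 2019 historical cohort, which has no stated source of utilities, and the sentences after the formula name a different comparator

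*Protocol*

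**What the plan says.** All of this is in the protocol.

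- **Model and cohort (Health economic analysis).** "Implementation cost and cost-effectiveness will be assessed in this trial following a pre-post economic model". The comparison group is then defined: "A historical cohort of all patients hospitalised for HF on a cardiology ward in 2019 in all participating centres will be assessed for comparison". Its data are described in one sentence: "Hospital bills and hospital administrative data based on the international classification of disease (ICD)-codes will be collected". Propensity matching is planned.
- **Refusals (same section).** "QOL and healthcare-related costs will be collected in selected patients refusing to participate in the smartphone intervention". Patient recruitment places their QOL questionnaire at 6 and 12 months, completed online. It states no baseline and names no instrument.
- **The ratio (same section).** The ICER is to compare costs with outcomes described as utilities. The printed formula subtracts the historical cohort in the numerator and again in the denominator.
- **The two sentences after the formula.** On cost: "The incremental cost represents the difference in total average cost per patient between the intervention group and the historical cohort or the participation refusals". On effect: "Effectiveness will be calculated by comparing QOL in the intervention group versus the participation refusals".
- **Elsewhere.** The Discussion says that "no distinct comparator group is available and a historical cohort will need to be used". The Sample size section calls the questionnaire group of at least 165 a non-randomised control group. Study endpoints lists demonstrating cost-effectiveness among the study objectives, ahead of the secondary clinical ones.

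**The concern.** An ICER answers one question: what does the intervention cost per unit of benefit relative to a given alternative? Both differences must therefore be taken against the same alternative. Here the formula names one alternative, the effectiveness sentence names another, and the cost sentence allows either. In addition, the alternative in the formula has no stated source for the outcome that the formula needs.

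Cost-effectiveness is a stated objective, and the Discussion links the economic results to possible reimbursement in Belgium. An analyst cannot follow all three statements at once. If they are left as they stand, the comparator has to be settled outside the protocol, possibly after costs are known, and the choice can decide whether the app appears to save or add cost per unit of utility.

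**Working it through.** The protocol states no ICER, cost or utility, so there is no figure to reproduce. The check is a matching of data to terms, followed by algebra.

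**Notation.** C is mean cost per patient and E is mean effectiveness in utilities. I is the intervention group, H the 2019 historical cohort, R the participation refusals.

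**Step 1. Which terms have a stated source?**

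| Term | Source in the protocol |
|---|---|
| C_I | cost data at the end of the trial (End-of-trial assessment; Table 2) |
| E_I | questionnaires including EQ5D (Table 2) |
| C_H | hospital bills and administrative data (Health economic analysis) |
| E_H | none stated |
| C_R | costs in selected refusals (Health economic analysis) |
| E_R | a QOL questionnaire, instrument not named (Patient recruitment; Health economic analysis) |

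The protocol does not say outright that the 2019 cohort will have no utilities. That follows from its list of sources, which includes no questionnaire, mapping or external utility values.

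**Step 2. Which ratios does the wording allow?**

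- Printed: P = (C_I − C_H)/(E_I − E_H). It cannot be computed, because E_H has no stated source.
- Refusals in both terms: S = (C_I − C_R)/(E_I − E_R). It is coherent, but it is not the printed formula.
- Mixed: M = (C_I − C_H)/(E_I − E_R). The cost and effectiveness sentences allow it, but it uses two comparators.

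**Step 3. How do they relate?**

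M − S = (C_R − C_H)/(E_I − E_R), so M = S only if C_H = C_R.

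M/S = (C_I − C_H)/(C_I − C_R), and the effectiveness term cancels. This quotient is negative exactly when C_I lies strictly between C_H and C_R. In that case M and S have opposite signs.

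M = P only if E_H = E_R (for C_I ≠ C_H).

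**Step 4. Illustration.** These values are assumed and are not in the protocol: C_I = 6000, C_H = 7000, C_R = 5500, and E_I − E_R from 0.02 to 0.05.

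- M = (6000 − 7000)/0.02 = −50,000, to (6000 − 7000)/0.05 = −20,000.
- S = (6000 − 5500)/0.02 = +25,000, to (6000 − 5500)/0.05 = +10,000.
- M/S = −1000/500 = −2 throughout.

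The example shows only that the sign can change. It says nothing about how likely that is in this trial.

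**The case against.** The strongest defence is the sentence that opens the ICER paragraph, which plans cost comparisons among the intervention group, the historical cohort and the refusals. In that light, the word 'or' in the cost sentence may mean one incremental cost per comparator rather than a free choice between them. Nothing in the text endorses the mixed ratio. This stands as far as cost is concerned: comparisons with both groups are already planned. It does not rescue the formula, whose effectiveness term still has no stated source and is contradicted two sentences later.

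It can also be said that effectiveness could be an outcome found in administrative data, such as rehospitalisation, on which the section concentrates. With the historical cohort in both terms, that would be a coherent ratio. But the paragraph specifies utilities and QOL, so it is not the ratio described.

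Three stronger readings are tempting and are not supported.

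- **That the mixed ratio is biased and the refusals-only ratio is not.** Equal mean costs are the condition for the two to agree, not for either to be unbiased. Refusals are self-selected. The matched 2019 cohort might represent usual-care cost better or worse, and the protocol does not decide this.
- **That differences in case mix would be credited to the app.** Propensity matching is planned for the 2019 cohort, so this cannot be presumed. The difference in calendar time remains.
- **That the data for a refusals-based utility ICER are already secured.** No utility instrument is named for refusals, and only selected refusals provide QOL and costs.

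**Conclusion.** The point holds as an internal contradiction. The printed utility ICER has no stated source for the historical cohort's effectiveness, and the following text names a different effectiveness comparator while leaving the cost comparator open. It is not a detail left to a statistical analysis plan, because no plan could follow the formula and both sentences together.

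The numerical size is unknown, since the protocol gives no costs or utilities. What is established is algebraic: the mixed and refusals-only ratios agree only when the two comparators have equal mean cost, and they differ in sign when mean intervention cost falls between them. The finding assumes that the listed data sources for the 2019 cohort are complete and that outcomes means utilities, as the paragraph says. It does not show which comparator is closer to the truth.

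A reader might add that End-of-trial assessment and Table 3 bring the WPAI into cost-effectiveness, whereas the Health economic analysis section counts direct intervention costs and care utilisation. That is a separate minor inconsistency about cost perspective and lends no support to this point.

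**What to change.** Rewrite the ICER paragraph so that each ratio has one named comparator in both terms.

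1. **Utility ICER.** Define it as (cost intervention − cost refusals)/(utility intervention − utility refusals), over the same time window. Confirm that the refusals' questionnaire yields a utility; EQ5D, already used in participants, would serve. Report the result as a non-randomised comparison with a self-selected group that has no stated baseline QOL.
2. **2019 cohort.** Keep the propensity-matched cohort for the cost comparison already planned. If a ratio is wanted, choose an effect that its administrative data contain, such as cost per rehospitalisation avoided, with that cohort in both terms.
3. **Pre-post sentence.** Align the statement about the pre-post economic model with this split.

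The cost is mainly rewording within the Health economic analysis section. A utility instrument may have to be specified in the questionnaire already planned for refusals. The drawback is that the utility ICER then rests on a self-selected comparator, with residual confounding that must be stated beside the result, and the 2019 cohort no longer contributes to it.

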patients must be in New York Heart Association (NYHA) class II, III, or IV with a left ventricular ejection fraction (LVEF) of ≤40%. The inclusion and exclusion criteria are shown in Table 1. A total of 165 patients will be included over 6 month. In total, 11 hospitals (local investigators) in Belgium with an HF clinic employing at least one certified HF nurse will be participating in patient recruitment. Patients are not randomised and will all be participating in the smartphone digital support intervention.

A screening register will be kept including reasons why eligible patients that do not participate are disregarding inclusion. Patients refusing participation will also be asked to complete a quality of life (QOL)-questionnaire at 6 months and 12 months which will be answered online. A total of 165 patients (who do not want to participate) will be asked to answer this questionnaire.

So the app will be made available to 165 patients for home monitoring and another group of 165 patients without an application will be asked to answer quality of life questionnaires.

Patients who agree to use the application can continue to use it after the study, if they wish.

Inclusion criteria	Exclusion criteria
Diagnosed with HF – NYHA class II-IV	Acute coronary syndrome
LVEF ≤40%.	High urgent listed for heart transplantation
Hospitalisation due to decompensated HF at the moment of inclusion or up to 1 week prior to inclusion (i.e. discharged ≤1 week prior to inclusion).	Planned revascularisation, TAVI, MitraClip and/or CRT implantation within 3 months after inclusion
Owning a smartphone and able to use an application	Known alcohol or drug abuse
Written informed consent obtained	Terminal renal insufficiency with haemodialysis or peritoneal dialysis
	Impairment or unwillingness to use the digital support equipment (e.g. dementia, impaired self-determination, lacking ability to communicate)
	Existence of any non-cardiac disease reducing life expectancy to less than 1 year
	Age <18 years
	Participation in other treatment studies or remote patient management programmes

Table 1 – Inclusion and exclusion criteria. NYHA: New York Heart Association. LVEF: left ventricular ejection fraction. CRT: cardiac resynchronisation therapy. TAVI: transcatheter aortic valve implantation.

Digital support platform

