Individual endpoints	Symptom control (NYHA, KCCQ-12), emergency department visits, length of hospital stay during the trial, unplanned CV readmission, all-cause mortality.

Table 3 - Study endpoints. CV: cardiovascular. SUTAQ: Service User Technology Acceptability Questionnaire. KCCQ-12: Kansas City Cardiomyopathy Questionnaire. EQ5D: EuroQol 5-dimension questionnaire. HeartQoL: Health-related quality of life questionnaire. PHQ9: patient health questionnaire-9. HLS-EU-Q16: European Health Literacy Survey Questionnaire. EHFSB-9: European Heart Failure Self-care Behaviour scale revised into a nine-item scale. SUTAQ: Service User Technology Acceptability Questionnaire. WPAI : work productivity and impairment. ICER: incremental cost-effectiveness ratio.

Statistical analysis

Sample size

A total of 165 patients will be included in the study. The sample size is based on comparable implementation trials (9,10). An additional patient group will be included that is not part of the study intervention but will complete questionnaires; this is a non-randomized control group. A minimum of 165 patients will take part in this control group for completion of the study.

Statistical analysis

The primary analyses will be paired Student *t*-tests and Wilcoxon signed-rank tests comparing baseline, 6-month and 12-month values for all patient-level outcomes. Secondary analyses aimed at determining the longitudinal impact of the smartphone digital support programme (i.e., using outcome data from the additional time points), and the correlation of independent variables (e.g., patient characteristics and adherence rates) with outcomes will be analysed using general linear mixed-model procedures. In addition, descriptive statistics will be produced for all variables collected, and subgroup analyses will be performed. All statistical analyses will be performed using the statistical software application SPSS (IBM Corporation, USA).

Descriptive statistics will be produced for the indicators of the implementation outcome to provide an objective measure of implementation success.

Discussion

The Bedicare-HF study is the first study that will investigate implementation of a smartphone-based HF digital support system in a real-life context on the background of European GDPR and medical device regulations.

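### Effectiveness in the health-economic analysis compares app users with self-selected refusers, with no adjustment stated, no baseline clinical or QOL data planned for refusers, and an ICER formula that names a different comparator

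*Protocol*

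**What the plan says.** **The contrast.** Under Health economic analysis, effectiveness is defined as follows: "Effectiveness will be calculated by comparing QOL in the intervention group versus the participation refusals". Patient recruitment states that there is no randomisation, and Sample size says of the refusers that "this is a non-randomized control group", with at least 165 of them beside 165 app users.

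**Confounding control.** The economic model is pre-post, and "A historical cohort of all patients hospitalised for HF on a cardiology ward in 2019 in all participating centres will be assessed for comparison", using hospital bills and ICD-coded administrative data. That paragraph ends: "Propensity matching will be applied". The next paragraph brings in the refusers and says nothing of matching or adjustment.

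**Data on refusers.** Three statements cover them:
- "Patients refusing participation will also be asked to complete a quality of life (QOL)-questionnaire at 6 months and 12 months which will be answered online" (Patient recruitment);
- "QOL and healthcare-related costs will be collected in selected patients refusing to participate in the smartphone intervention" (Health economic analysis);
- "A screening register will be kept including reasons why eligible patients that do not participate are disregarding inclusion" (Patient recruitment).

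Table 2, which lists NYHA class, laboratory tests, echocardiography and the questionnaires at baseline and month 6, describes the visits of the intervention group.

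**The ICER.** The same section says: "Costs and outcomes (utilities) will be compared by calculation of the incremental cost-effectiveness ratio (ICER"). The formula that follows subtracts the historical cohort in both the cost term and the effectiveness term. The text after it lets the cost difference be taken against the historical cohort or the refusers, and takes effectiveness from the refusers.

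**The statistical section.** It gives paired tests across baseline, month 6 and month 12, and a mixed model for the programme's longitudinal impact and for correlates of outcome. No comparison of acceptors with refusers is stated.

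**The concern.** Patients who take up a self-management app may differ in health, motivation and digital skill from those who decline it. Without adjustment, any such difference in month-6 QOL goes straight into the effectiveness term and is credited to the app. The same holds for the cost difference when it is taken against refusers.

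The main difficulty is data collection. A model can be written later, but it cannot use baseline values that nobody recorded. With no QOL score at entry, even a comparison of changes from baseline is impossible between these groups.

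Demonstrating cost-effectiveness is a stated objective, and the Discussion ties a successful result to reimbursement in Belgium. An ICER that mixes selection with effect, or takes its two terms from different comparators, would be weak support for that decision.

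**Working it through.** **1. Which planned data could support an adjustment?**

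| Item | App users | Refusers |
|---|---|---|
| QOL at baseline | Table 2 | not planned |
| QOL at month 6 | Table 2 | online |
| QOL at month 12 | re-evaluation | online |
| NYHA class, LVEF (echocardiography), creatinine | Table 2 | not planned as recorded data |
| Healthcare costs | yes | in some refusers |
| Reason for refusal | does not apply | screening register |
| Hospital, ICD and billing data | yes | probably obtainable where costs are collected |

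The clinical covariates and the entry score are missing on one side only. The eligibility criteria limit the range of LVEF and NYHA class in both groups, but they do not balance the groups within that range.

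**2. Does any stated analysis make the contrast?** The paired tests compare a patient with himself or herself and cannot compare two groups. The mixed model names patient characteristics and adherence as independent variables, and states no group term. The matching sentence, as placed, belongs to the 2019 cohort.

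**3. Which comparator does the ICER use?**

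| Place in Health economic analysis | Cost comparator | Effectiveness comparator |
|---|---|---|
| ICER formula | historical cohort | historical cohort |
| Text after the formula | historical cohort or refusers | refusers |

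Only bills and administrative data are planned for the 2019 cohort, so its effectiveness term cannot be filled with QOL. If the refusers fill it while the cost term stays with 2019, the ratio combines two different contrasts.

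**4. Size (illustration).** The protocol gives no effect size, SD or power, so there is no figure of its own to reproduce. Inputs: 165 per group (Sample size); a true app effect of zero (assumed); a selection gap d in SD units of month-6 QOL (assumed); complete responses (assumed); a two-sided test at 0.05 (assumed, because the protocol states no test here).

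SE = sqrt(1/165 + 1/165) = sqrt(2/165) = 0.110

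P(significant) = Φ(d/SE − 1.96) + Φ(−d/SE − 1.96)

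- d = 0.125: d/SE = 1.135, P = 0.206.
- d = 0.25: d/SE = 2.271, P = 0.622.
- For range: d = 0.1 gives 0.149, d = 0.2 gives 0.443, d = 0.3 gives 0.778. With no gap P = 0.05.

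A larger sample would shrink the SE and leave the gap in place, so it would not help.

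**5. On the ICER scale (illustration).** An assumed utility gap u from selection alone, held for half a year, credits an app without effect with u × 0.5 QALY. Per assumed EUR 1,000 of incremental cost:

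- u = 0.02: 0.010 QALY, ICER 1,000/0.010 = EUR 100,000.
- u = 0.05: 0.025 QALY, ICER 1,000/0.025 = EUR 40,000.
- u = 0.10: 0.050 QALY, ICER 1,000/0.050 = EUR 20,000.

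The true ratio is undefined in each case, because the true QALY gain is zero.

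**The case against.** The best defence has four parts.

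**An analysis plan may supply the model.** Covariates and weighting for a non-randomised secondary contrast are commonly settled there, and none is at hand. This stands for the missing model taken alone. It does not reach the missing data, which the protocol itself fixes.

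**The text never says unadjusted.** A reader might infer that a crude comparison is prescribed and that matching is ruled out for refusers. The documents do not say so. The matching sentence carries no explicit restriction, and tying it to the 2019 cohort rests on its position. If it were meant to cover refusers, the listed data would still contain no clinical covariates or entry QOL to match on.

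**Refusers are not a blank.** A reader might also infer that no adjustment at all is possible. That goes too far. The register is kept *including* reasons, which does not exclude other fields; the Discussion expects information on refusers to be available; and costs come from hospital billing departments, so hospital and some coded diagnoses are probably known where costs are collected. The gap concerns NYHA class, LVEF, renal function and baseline QOL.

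**Direction and test.** It is tempting to say that the bias favours the app, or that refusal depends on how each hospital presents it. Nothing in the protocol supports either statement. No significance test is stated for this contrast, so the percentages above describe a test that someone might run.

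The protocol does label the group as non-randomised and admits that it lacks a distinct comparator. It does not discuss self-selection among refusers.

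**Conclusion.** The point holds for the health-economic analysis. Effectiveness rests on a contrast between groups formed by choice, no adjustment is stated for it, and the listed refuser data would not allow adjustment for NYHA class, LVEF, renal function or baseline QOL. The ICER formula and the text after it also name different comparators for effectiveness, and the formula's comparator has no planned QOL.

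The size cannot be derived from the protocol. With 165 complete responses per group and no app effect, an assumed gap of 0.125 SD would appear nominally significant about 21% of the time, and one of 0.25 SD about 62%. Both gaps are assumptions, and their direction is open.

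A reader might infer that the trial's main QOL result is undermined in the same way. It is not: the primary analysis is a paired comparison within patients and does not use the refusers. This should be changed before data collection from refusers begins, because the missing baseline QOL cannot be recovered afterwards.

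**What to change.** 1. **Data.** For each refuser who agrees to the questionnaire, record at screening, from the existing file: age, sex, hospital, NYHA class, LVEF, renal function, diabetes and admissions in the prior year. Add the QOL questionnaire at entry. Give the register entry and the online answers a common code so that they can be joined; the protocol describes such coding only for app users. State how the refusers for cost collection are chosen.
2. **Analysis.** In Health economic analysis and Statistical analysis, state a propensity-weighted or covariate-adjusted comparison of month-6 QOL and cost that includes these covariates, entry QOL and hospital. Report it as an adjusted association and not as an effect of the app. Say whether the matching sentence applies to the 2019 cohort, the refusers or both.
3. **ICER.** Reconcile the formula with the sentence that names the refusers, so that cost and effectiveness use the same comparator.

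**Cost.** A few register fields, one questionnaire, consent wording for refusers and one extra model; no extra visit. Asking more of refusers may lose some of them. Adjustment will not remove unmeasured willingness. Unwillingness to use the equipment is itself an exclusion criterion, so some refusers may fall outside the eligible population. Both should be stated as limitations.
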